**PARTNERS HUMAN RESEARCH COMMITTEE
PROTOCOL SUMMARY**

Answer all questions accurately and completely in order to provide the PHRC with the relevant information to assess the risk-benefit ratio for the study. Do not leave sections blank.

PRINCIPAL/OVERALL INVESTIGATOR

[name]

PROTOCOL TITLE

Treatment of Field Cancerization for Reduction in Tumor Burden – A Prospective Study

NCT NUMBER

NCT02150863

FUNDING

Wellman Center for Photomedicine

VERSION DATE

December 28, 2016

SPECIFIC AIMS

Concisely state the objectives of the study and the hypothesis being tested.

This project aims to treat field cancerization in a manner that will reduce the tumor burden in patients with significant photodamage

1. To demonstrate that we can reduce the non melanoma skin tumor burden over time by treating the entire field of actinic keratoses and atypical keratinocytes.
2. To compare the efficacy and side effects of ablative CO2 laser resurfacing vs. ablative CO2 laser resurfacing plus post treatment suction blister epidermal grafts vs. control (no intervention).
3. To demonstrate a reduction in the number of actinic keratoses over time
4. To demonstrate an improvement in clinical appearance of the treatment area
5. To demonstrate a reduction in the degree of P53 mutations seen with histopathology
6. To demonstrate that subjects tolerate the treatment with few side effects
7. To demonstrate increased telomere length in treated areas

BACKGROUND AND SIGNIFICANCE

Provide a brief paragraph summarizing prior experience important for understanding the proposed study and procedures.

Field cancerization is a risk for any individual with excessive and prolonged sun exposure, immunosuppression, or exposure to radiation or carcinogens. We are very good at treating the skin cancer but if we leave behind the atypical field of keratinocytes it is only a matter of time

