The proposed pilot study is a 3 year prospective, randomized, controlled comparison of a single treatment with carbon dioxide laser resurfacing vs. carbon dioxide resurfacing plus autologous epidermal skin graft from a non sun exposed site vs. control. Thirty subjects will receive treatment with each of the modalities on randomly-assigned portions of the treatment area. The primary measures of efficacy are (a) count of the number of actinic keratosis and non melanoma skin cancers, (b) blinded evaluation of severity from standard digital photographs taken before and after the treatments, and (c) change in histology before and after treatment: seen by grading and change of p53 immunostaining. Other study endpoints include time point to the next skin cancer is found in the treatment area, overall clinical appearance, change in mutant P53 of skin samples, and telomere length variability.

Safety measures include (a) pain, (b) scarring, (c) wound healing, (d) and infection

Subjects will be recruited through advertisements posted within the hospital(s), outpatient dermatology clinics and partners electronic mail.

Inclusion criteria

1. Subjects with ages between 18 and 85 years, male or female.
2. Subjects with at least 4 clinically diagnosed AKs per treatment site (up to 200 sq cm), excluding the face.
3. Subjects with history of at least 1 skin cancer within the past year
4. Willingness to participate in the study
5. Informed consent agreement signed by the subject
6. Willingness to follow the treatment schedule and post treatment care requirements
7. Willingness to not use topical or systemic (oral) TREATMENT medications including imiquimod, 5 Fluorouracil, photodynamic therapy, during the treatment period.
8. Has not had treatment for AKs in the treatment area for 4 weeks prior to enrollment

Exclusion criteria

1. Subjects with active skin cancer in the treatment area. Once the non-melanoma skin cancer has been treated, the subject can be immediately enrolled.
2. Infection of the area to be treated
3. An open wound in the area to be treated
4. Presence of suntan in the area to be treated, or active tanning during the study
5. Subjects who have taken medication known to induce photosensitivity in the previous 3 months
6. The patient has any contraindication to use of the CO2 laser
7. Subject is unable to comply with treatment, home care or follow-up visits
8. Subject is pregnant or breast feeding

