- II) Exam of the treatment area: AK count, evaluate for clinically appearing NMSC present; evidence of scarring, evidence of infection; evidence of healing . Also will get history from patient: visits to dermatologist? and treatments rendered? Will also review medical records to confirm the history.
- III) 6 scouting epidermal biopsies, using shave biopsy technique (from the treatment area) for histology and immunostaining. Will also bank a portion for PCR at the end of the study.
- IV) Adverse event evaluation
- V) Investigator assessments: wound assessment, overall clinical appearance

Follow-up Visits(6 months, 1 year, 1.5 year, 2 year, 2.5 year) (lasting 30 minutes each)

- I) Photography
- II) Exam of the treatment area: AK count, evaluate for clinically appearing NMSC present; evidence of scarring, evidence of infection; evidence of healing . Also will get history from patient: visits to dermatologist? and treatments rendered? Will also review medical records to confirm the history.
- III) Adverse event evaluation
- IV) Investigator assessments: overall clinical appearance

End of Study visit (3 year) (lasting 1.5 hours)

Patients will exit the study after 3 years

- II) Photography
- III) Exam of the treatment area: AK count, evaluate for clinically appearing NMSC present; evidence of scarring, evidence of infection; evidence of healing . Also will get history from patient: visits to dermatologist? and treatments rendered? Will also review medical records to confirm the history

- IV) **6 scouting epidermal biopsies, using shave biopsy technique (from the treatment area) for histology and immunostaining. Will also bank a portion for PCR at the end of the study.
- V) Adverse event evaluation
- VI) Investigator assessments: overall clinical appearance

** During the course of the study, the subjects will have a total of 18 scouting epidermal biopsies using the shave biopsy technique

Evaluation of Safety and Efficacy

Assessed by investigators (non-blinded) and by blinded evaluators (clinical photographs), periodically for 3 years after a single treatment session.

Reported by the Patients

Specific form is attached.

I. Side effects reported by the patient:

To assess major and minor side-effects, patients will be asked for each treatment site to fill in the following sentence for each test site: **“The side effects I experienced after the treatment were:”** E.G.

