Table I. **N/A:** Did not have this side effect / **1:** Mild / **2:** Moderate / **3:** Severe

A. Blistering	N/A	1	2	3
B. Scarring	N/A	1	2	3
1. Swelling	N/A	1	2	3
2. Redness	N/A	1	2	3
3. Scabs (crusting)	N/A	1	2	3
4. Weeping skin (pustulation)	N/A	1	2	3
5. Scaling or flaking skin (exfoliation)	N/A	1	2	3
6. Itchy skin	N/A	1	2	3
7. Erosion (ulceration)	N/A	1	2	3
8. Tanning	N/A	1	2	3
9. Lightening of the skin	N/A	1	2	3
11. Wheals	N/A	1	2	3
12. Bleeding	N/A	1	2	3
13. Folliculitis/ Acne	N/A	1	2	3
14. Oozing	N/A	1	2	3
15. Change in sensitivity/numbness	N/A	1	2	3

[figure not shown]
I. Pain assessment - Visual Analog Scale (VAS).

The VAS will be completed by study subject immediately after the treatment, and at each procedure follow up visit (Day 3, Day 7, week 4)

Pain is any of the following: sensation of tingling, stinging, prickling, or burning feeling, heat under the skin, tenderness, mild, moderate or severe pain).

Specific VAS form is attached

Patients will be asked to circle the number below that most closely corresponds to pain associated with their DISEASE.

Reported by the Investigators and Blinded-evaluators

Reported by the Investigator

Specific form is attached.

Investigator's Wound Assessment

Table 2. N/A: Did not have this side effect / 1: Mild / 2: Moderate / 3: Severe

A. Blistering	N/A	1	2	3
B. Scarring	N/A	1	2	3
1. Swelling	N/A	1	2	3
2. Redness	N/A	1	2	3
3. Crusting	N/A	1	2	3
4. Pustulation	N/A	1	2	3
5. Scaling or flaking skin (exfoliation)	N/A	1	2	3
6. Erosion (ulceration)	N/A	1	2	3
7. Hyperpigmentation	N/A	1	2	3
9. Hypopigmentation	N/A	1	2	3
10. Urticaria	N/A	1	2	3
11. Infection	N/A	1	2	3
12. Folliculitis/ Acne	N/A	1	2	3
14. Oozing	N/A	1	2	3

--	--

Overall Appearance Scale (blinded MD to complete with photos)

- Physicians will consider both cosmetic appearance but also the degree of photodamage and clinical atypia.

	Co2 treatment site	Co2 + epidermal graft Treatment site	Control site
Excellent	 5	 5	
Good	 4	 4	
Satisfactory	 3	 3	
Poor	 2	 2	
Unacceptable	 1	 1	

End points:

- AK count
- NMSC count
- change in overall clinical appearance
- time to healing

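### The pain VAS and the investigator's wound form are not tied to a site, so Aim 2's within-subject comparison of pain and wound grade is not secured

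*Protocol*

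**What the plan says.** The design is within subject. Under Research Design and Methods: "Thirty subjects will receive treatment with each of the modalities on randomly-assigned portions of the treatment area". Specific Aims, item 2, sets the purpose: "To compare the efficacy and side effects of ablative CO2 laser resurfacing vs. ablative CO2 laser resurfacing plus post treatment suction blister epidermal grafts", with an untreated control as the third condition. The same design section lists what counts as safety: "Safety measures include (a) pain, (b) scarring, (c) wound healing, (d) and infection". The background adds a hypothesis that grafting helps the wound heal after CO2.

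Four instruments bear on this.

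- **Patient side-effect report (Table I).** It is explicitly per site: "patients will be asked for each treatment site to fill in the following sentence for each test site". The visit grid schedules it at Day 3, Day 7 and Week 4.
- **Overall Appearance Scale.** It is printed with three columns: CO2, CO2 plus graft, control.
- **Pain VAS.** "The VAS will be completed by study subject immediately after the treatment", and then at Day 3, Day 7 and Week 4. The subject circles one number for pain linked to their DISEASE, a word left in capitals. No site is named. The form is said to be attached.
- **"Investigator's Wound Assessment" (Table 2).** It has one N/A-1-2-3 answer per item, with no site field, site columns or instruction to repeat it by site. It is scheduled at Day 3, Day 7, Week 4 and Month 3. The form is said to be attached.

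**The concern.** When every subject receives every condition, a safety measure informs the comparison only if it records which portion of skin it describes. In a parallel-group trial one pain score per subject belongs to one arm. Here it belongs to all three conditions at once, and no later analysis can divide it.

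Pain is the most exposed outcome. The VAS is the only pain instrument, because Table I has no pain item. By Day 3 a subject has lasered skin, lasered and grafted skin, a donor-site wound and the sites of six baseline shave biopsies. One number mixes these sources. Read literally, the DISEASE wording does not ask about the treatment at all.

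Infection comes next. It is an item on Table 2 but not on the patient's form, so the only graded infection record is the one without a site label. Investigator-graded scarring has the same gap, and Table 2 continues to Month 3 while the patient's form stops at Week 4. The contrast most at risk is CO2 against CO2 plus graft, on which the graft hypothesis rests.

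**Working it through.** No stated figure needs reproducing: the protocol gives no power, effect size or standard deviation for these outcomes, and the point does not depend on them. The check sets the instruments side by side and counts the records.

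**Instruments compared**

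| Instrument | Per-site instruction | Site columns | Pain item | Infection item | Scarring item | Scheduled |
|---|---|---|---|---|---|---|
| Patient report, Table I | yes | no | no | no | yes | Day 3, Day 7, Week 4 |
| Overall Appearance Scale | by layout | yes, three | no | no | no | baseline to 1 year and 3 years in the grid |
| Pain VAS | no | none described | yes | no | no | after treatment, Day 3, Day 7, Week 4 |
| Wound assessment, Table 2 | no | no | no | yes | yes | Day 3, Day 7, Week 4, Month 3 |

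Every pain score and every infection grade comes from an instrument with neither a per-site instruction nor site columns. Scarring is graded on one instrument that is per site and one that is not.

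**Does other text supply the missing site?** The follow-up visit lists examine scarring, infection and healing for the treatment area as a whole. The section on data and safety monitoring notes later treatments for the treatment area and the control. That separates treated from untreated skin but not CO2 from CO2 plus graft. Time to healing is a listed endpoint, yet healing too is examined for the whole area.

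**Counts**, assuming 30 treated subjects and full attendance:

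- Pain, one entry per time point: 30 x 4 = 120 scores. The Day 0 score is taken from the VAS text and the treatment-visit list.
- Wound assessment, one entry per visit: 30 x 4 = 120 forms.
- Either instrument recorded by site: 30 x 3 x 4 = 360 site-level records, or 30 x 3 = 90 per visit, which is 30 within-subject triplets.

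One entry per visit gives 30 values per visit and no within-subject contrast between conditions. One entry per site gives up to 30 triplets. The protocol does not say which applies to Table 2. For the VAS, the printed instruction points to the first.

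**The case against.** The strongest reply is that form layout proves little. Table I has the same single answer column as Table 2, yet the text says it is completed for each test site. So this protocol does print one column for a form used once per site, and Table 2 may be meant the same way. The protocol nowhere says that either form is completed once per subject. Both forms are described as attached and are not in the text, and a figure just above the VAS section is not shown.

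This stands, and it limits the conclusion for Table 2. It does not remove the point. Table I carries a written per-site instruction that Table 2 and the VAS lack, and the VAS wording asks for one number about the disease.

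A second reply is that site information survives elsewhere. Photographs are scheduled at every visit from baseline, tracings are made as needed, and adverse events are evaluated at each visit from baseline and entered in REDCap. These may place a visible scar or infection. This is fair for visible events, although the protocol does not say that adverse event records name the site. It does not help for pain, which no photograph shows.

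A reader might go further and infer that Aim 2's side-effect comparison cannot be made at all, or that nothing records which portion was affected. The documents do not support that. The patient report is per site and covers scarring, blistering, erosion, oozing and other effects to Week 4.

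**Conclusion.** The point holds as a gap in what the protocol specifies. Pain is the firmer part: with the VAS completed as worded, up to 120 scores carry no site and cannot be compared between modalities. For Table 2, up to 120 assessments have no stated site, so the comparison of investigator-graded outcomes is not secured. It might still be recovered if the form is in practice repeated for each site.

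The conclusion assumes that the attached forms match the printed text. The counts also assume 30 treated subjects and complete attendance. If the attached forms already ask for each site separately, the remaining fault is protocol text that does not say so, together with the DISEASE wording if that also appears on the form.

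It should be corrected before data are collected, because an unlabelled pain score cannot be repaired afterwards.

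**What to change.** 1. Ask for one VAS score for each of the three sites (CO2, CO2 plus graft, control) at each VAS time point, and replace the DISEASE wording with pain at the named site.
2. Give Table 2 the three site columns already used on the Overall Appearance Scale.
3. State in the protocol that pain and wound grades are compared between sites within subject.

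The cost is a change to the REDCap form layout and a few sentences of protocol text. At each visit where an instrument is used, it would have three sets of entries instead of one. Subjects may find it hard to separate pain between adjacent portions, so some blurring between the two lasered sites should be expected. That is still more informative than a score with no site.

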Provide a brief description of any foreseeable risks and discomforts to subjects. Include those related to drugs/devices/procedures being studied and/or administered/Performed solely for research purposes. In addition, include psychosocial risks, and risks related to privacy and confidentiality. When applicable, describe risks to a developing fetus or nursing infant.

Foreseeable Risks and Discomforts of Ablative CO2 laser

	Common	Uncommon
Major:		
1. Severe Pain (Pain 8/10 or higher on VAS scale)		x
2. Blistering (with potential for secondary infection)		x
3. Ulceration (deep erosion, deep wound) with scarring		x
4. Blindness (There is a risk of blindness from the CO2		X

laser. Everyone in the room will wear protective goggles or corneal shields at all times during the treatment to prevent eye injury.)		
Minor:		
1. Mild to Moderate Pain (Pain 1-7/10 on VAS scale) (tenderness) (tingling, stinging, prickling, or burning feeling, tenderness)	x	
Topical anesthesia plus cooling air (Zimmer) will decrease pain during treatment.		
During the treatment we will be asking the patient to rate their level of pain according to the visual analog pain scale that will be provided and explained to them. If at any time during the procedure the patient indicates a pain level of 7 or above based on the visual analog pain scale laser treatments will stop and use intralesional 1% lidocaine for anesthesia in the treatment area		
2. Swelling (edema)	x	
3. Redness (erythema)	x	
4. Crusting (scabbing)	x	
5. Pustulation (weeping skin)	x	
6. Exfoliation (scaling or flaking skin)	x	
7. Itchy Skin	x	
8. Ulceration (erosion)	x	
9. Tanning (pigmentation)< 3 months	x	
10. DISEASE flare		x
11. Hypopigmentation (lightening of the skin)	x	
12. Minor Blistering (vesiculation)		x
13. Wheals		x
14. Bleeding	x	
15. Folliculitis/ acne		x
16. Oozing	x	
17. Dysesthesia (change in sensitivity, numbness)		x
18. Infection: The area may become infected; however, keeping the site clean and using the petroleum ointment should prevent this. If the site does become infected, the patient may need to take oral antibiotics. Signs of infection include redness or swelling lasting longer than 3 days, oozing, or fever. If the patients experience any of		x

these symptoms, they will be instructed to contact the study doctor for immediate evaluation. Oral valacyclovir and dicloxacillin will be given to the patients to prevent the risk of herpes virus related complications.		
19. Milia		X

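### The pain scale instruction asks about pain from the patient's disease, although the protocol uses the scale for pain after treatment; the schedule table also leaves out the Day 0 score that the text requires

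*Protocol*

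**What the plan says.** The protocol's section headed Pain assessment - Visual Analog Scale (VAS) contains four relevant statements.

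- Timing: "The VAS will be completed by study subject immediately after the treatment, and at each procedure follow up visit", which it lists as Day 3, Day 7 and Week 4.
- Definition: "Pain is any of the following: sensation of tingling, stinging, prickling, or burning feeling, heat under the skin, tenderness", followed by pain of any grade. No cause is named.
- Form: "Specific VAS form is attached". The form is not among the pages at hand.
- Instruction to the patient: "Patients will be asked to circle the number below that most closely corresponds to pain associated with their DISEASE".

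Elsewhere, Research Design and Methods states "Safety measures include (a) pain, (b) scarring, (c) wound healing, (d) and infection". The table of foreseeable risks of the ablative CO2 laser lists "Severe Pain (Pain 8/10 or higher on VAS scale") as a major risk and "Mild to Moderate Pain (Pain 1-7/10 on VAS scale) (tenderness) (tingling, stinging, prickling, or burning feeling, tenderness") as a minor one. The minor entry adds that patients will rate their pain on the same scale while the laser is in use. The same table also contains the entry "DISEASE flare".

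For Day 0, the Part II (Treatment) visit list has pain as its item V, a patient assessment. In the schedule table, the Day 0 row is blank under the pain scale column.

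**The concern.** A patient-completed scale measures what its instruction asks for. This one names the disease as the source of pain, while the protocol otherwise treats the scale as a measure of how the procedure was tolerated.

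Neither structured side-effect list (the patient's Table I and the investigator's Table 2) has a pain item. The VAS is therefore the only structured pain score described after treatment. At stake are aim 6 (that subjects tolerate the treatment) and the side-effect part of aim 2, which compares laser, laser plus graft, and control.

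The Day 0 gap concerns the score taken closest to the procedure.

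**Working it through.** The protocol states no figure to reproduce. The check compares its statements and counts time points.

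**1. Which pain is meant?**

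| Place in the protocol | What it implies |
|---|---|
| VAS instruction | Pain from the disease |
| VAS timing | Pain after treatment: first post-treatment score straight after the procedure, last at Week 4 of a 3-year follow-up, no pre-treatment score listed |
| Safety measures, item (a) | Pain as a harm, alongside scarring, wound healing and infection |
| Laser risk table | Pain caused by the laser, graded 1-7 (minor) and 8 or higher (major) out of 10 |
| Laser risk table, rating during treatment | Pain caused by the laser |
| Patient side-effect item | Effects experienced after the treatment, asked for each site |
| VAS definition of pain | Neutral: no cause given |

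One statement points to the disease, five point to the treatment and one is neutral. A scale meant for disease pain would be expected to have a pre-treatment value and scores over the long follow-up; this one has neither.

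**2. Where does the word come from?** The capitalised word DISEASE occurs twice in the protocol: in the VAS instruction and in the laser risk table. Elsewhere the condition is named (actinic keratoses, field cancerization). An unfilled template word is the likely explanation. The contradiction does not depend on it, because putting the name of the condition in its place would still point the patient to the wrong source of pain.

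**3. What would the literal reading do?** Let w be the pain after treatment and d the disease pain, both out of 10. The intended score is w, the literal score is d, and the error is d − w. The protocol gives no value for d, so the range has to be shown:

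- d = 0: the error is −w. The recorded score is 0 whatever the wound pain, so pain in the major band (w of 8 or more) would be recorded as none.
- d = w: there is no error.
- d > w: pain after treatment is overstated.

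Tolerability looks too favourable whenever d is below w.

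**4. Time points.**

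- Text: straight after treatment on Day 0, Day 3, Day 7, Week 4 = 4 post-treatment scores. The rating during the laser procedure is a further use of the scale and is not in this count.
- Table: Day 3, Day 7, Week 4 = 3 scores.
- Difference: 4 − 3 = 1, the Day 0 score.

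The gap does not look like a shifted row. The table header has 13 columns. The Day 0 row has 1 label, 1 blank (consent), 8 marks (pregnancy test through adverse events) and 3 blanks: 1 + 1 + 8 + 3 = 13. Moving the marks one column to the right would fill the pain column but remove the pregnancy test, which the Day 0 list requires.

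**5. Reach.** Pain is 1 of 4 listed safety measures and 0 of 6 listed endpoints (AK count, NMSC count, overall appearance, time to healing, p53, telomere length).

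**The case against.** The strongest objection is that the patient reads the attached form, not the protocol sentence, and the form may be correct. The setting also helps: the scale is handed over straight after treatment, a neutral definition of pain comes first, and for the rating during treatment the protocol says the scale will be explained. This stands in part. Actual mis-measurement is not shown. The sentence still conflicts with the protocol's own use of the scale, and if the form is right, then form and protocol disagree.

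A second objection is that the blank Day 0 cell is a slip in a summary table already covered by the Day 0 visit list and the VAS section. That stands as to consequence: staff who follow the visit list would collect the score. The table and the text still need to agree.

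A third is that this is only an editorial matter. Most of the weight of that objection is accepted in the verdict, but the sentence is an operative instruction for a named safety measure, and scores taken under a wrong question cannot be repaired afterwards.

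A reader might go further and infer that the form fails to score the laser, graft and donor sites separately, or that the scale has no bearing on the control site. The documents support neither. The form is not shown. The control portion receives no intervention, but the modalities are assigned to portions of the treatment area and baseline biopsies are taken there, so whether the control portion is biopsied is not settled.

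**Conclusion.** The point holds. The VAS instruction contradicts the timing, the safety role and the risk grading that the protocol gives the same scale, and the schedule table omits one of the 4 post-treatment scores the text requires.

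The impact is low. It is confined to the description of tolerability under aim 6 and the side-effect comparison in aim 2. Adverse events are still recorded at Day 0 and every later visit, though that is not a graded pain score.

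A too favourable pain result assumes that patients follow the wording literally, that their disease pain is lower than their wound pain, and that the form carries the same wording. None of these can be confirmed from the protocol.

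A reader might infer that the pain data are invalid, that the Day 0 score will not be collected, or that an efficacy result is affected. The documents do not support this: the form is unseen, the Day 0 visit list asks for the score, and pain is not an endpoint.

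**What to change.** 1. Replace the phrase about disease with wording that ties the score to pain after the study treatment.
2. State whether pain from the baseline shave biopsies and from the graft donor site is included. The 6 baseline biopsies are taken on the treatment day or, if baseline is held separately, within 2 weeks of it, and the risk tables list pain for both biopsy and grafting.
3. Make the protocol sentence and the attached form agree. Because aim 2 compares side effects between conditions, also state which site or sites a score refers to.
4. Mark the pain scale cell in the Day 0 row, labelled as the score straight after treatment, so that table and text both give 4 post-treatment scores.
5. If any subject has already been scored under the present wording (the protocol does not say), flag those scores as collected under it.

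The cost is one reworded instruction with a short scope statement, one table mark and one look at the form. No visit or assessment is added.

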All source data will be organized and entered onto RedCap (www.redcap.partners.org). Any pertinent notes to file regarding the subject and their study visit will be documented by the study coordinator and kept in the applicable subject-file on RecCAP. All subjects will be assigned a study identification number. We will pre-test/pilot test the source documents on RedCap prior to enrolling any subjects to ensure confidentiality and effectiveness. The source documents on RedCap will only be accessible to study staff by a special login/password. The surveys will be accessible by invitation only with a special login/password. RedCap documents will not be accessible to the public. There will be no bias to conducting research using RedCap because all surveys will be completed by the patient while he or she is at the study visit. We will use computers and internet at Wellman Center for Photomedicine for the completion of these documents.

This study will be performed in accordance with the Declaration of the World Assembly, 1975, Tokyo (Fed. Reg. 40, 16056, April 9, 1975) and the "Guiding Principles for Human Studies" of the Massachusetts General Hospital. These guidelines will be followed specifically with regard to the privacy and confidentiality of patient care and study records.

SENDING SPECIMENS/DATA TO RESEARCH COLLABORATORS OUTSIDE PARTNERS

Specimens or data collected by Partners investigators will be sent to research collaborators outside Partners, indicate to whom specimens/data will be sent, what information will be sent, and whether the specimens/data will contain identifiers that could be used by the outside collaborators to link the specimens/data to individual subjects.

N/A

Specifically address whether specimens/data will be stored at collaborating sites outside Partners for future use not described in the protocol. Include whether subjects can withdraw their specimens/data, and how they would do so. When appropriate, submit documentation of IRB approval from the recipient institution.

N/A

RECEIVING SPECIMENS/DATA FROM RESEARCH COLLABORATORS OUTSIDE PARTNERS

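### The form for the blinded photographic rating of overall appearance names each site's treatment, so completing it as printed unblinds the rater

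*Protocol*

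**What the plan says.** Each subject contributes three sites: CO2 laser, CO2 laser plus epidermal graft, and untreated control. These are assigned at random to portions of the treatment area (Protocol, Research Design and Methods).

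The section Evaluation of Safety and Efficacy divides the assessors into two groups: "Assessed by investigators (non-blinded) and by blinded evaluators (clinical photographs), periodically for 3 years after a single treatment session". The section Data and Safety Monitoring adds that blinded investigators carry out the overall efficacy assessments.

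The rating form is titled "Overall Appearance Scale (blinded MD to complete with photos". It is a five-category scale from unacceptable to excellent, and the rater is to weigh cosmetic appearance, photodamage and clinical atypia together. One printed column is headed "Co2 + epidermal graft Treatment site". The other two are headed, just as openly, as the CO2 site and the control site.

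The End points list includes "change in overall clinical appearance". Research Design and Methods gives as primary measure (b) the "blinded evaluation of severity from standard digital photographs taken before and after the treatments". The same paragraph then says: "Other study endpoints include time point to the next skin cancer is found in the treatment area, overall clinical appearance".

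On data handling, Privacy and Confidentiality says: "All source data will be organized and entered onto RedCap". It also gives each subject a study identification number and says that the electronic source documents will be piloted before enrolment. It does not mention codes for sites or photographs.

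**The concern.** A rater cannot be blinded to treatment and also enter scores under headings that state the treatment. To put a score in the right column, the rater has to know which photographed site is which. The form as printed therefore defeats the blinding that its own title claims.

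This matters because the rating is a subjective judgement and the protocol states its expectations. The Background hypothesises that grafts will help healing, and Data and Safety Monitoring expects control sites to improve less than treated ones. A rater who shares those expectations and sees the treatment name can shift a score without intending to. The result could not then properly be reported as a blinded assessment.

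The contrast most exposed is the one in aim 2: "To compare the efficacy and side effects of ablative CO2 laser resurfacing vs. ablative CO2 laser resurfacing plus post treatment suction blister epidermal grafts". Both of those sites are lasered, so laser effects alone do not tell them apart. The column heading does.

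**Working it through.** No formula applies. The protocol gives no figure on this point to reproduce, and the size of the bias cannot be derived from it. The check sets the relevant places side by side.

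1. **Who rates, and from what.** The form's title says a blinded physician working from photographs. Evaluation of Safety and Efficacy agrees that the photographic evaluators are the blinded group.

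2. **What the form shows the rater.** It has three columns, and each heading names the condition applied to that site. That is 3 of 3 headings disclosing allocation.

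3. **What is needed to complete it.** Comparison is within subject, so the masking that matters is at site level. A score can be entered correctly only after the photograph has been matched to a treatment. If the rater makes that match, the rater is unblinded. If someone else makes it, a coded intermediate step is needed.

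4. **Is such a step stated?** Design, visit procedures, schedule, evaluation, monitoring and confidentiality were read for one. None mentions neutral site labels, masked or reordered photographs, concealed visit dates, a key holder or transfer from a coded reading. The only code is the subject identifier. It protects confidentiality and does not hide which site within a subject had which treatment.

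5. **How often the scale is used.** As the schedule table reads, the scale is marked at eight visits: baseline, Day 3, Day 7, Week 4, 3 months, 6 months, 1 year and 3 years. The problem is not confined to a single reading.

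6. **Who else rates appearance.** From Day 3 to the 3-year visit, the visit procedures list overall clinical appearance under investigator assessments, and Evaluation of Safety and Efficacy calls the investigators non-blinded. Two ratings of the same attribute may therefore exist, and only one of them is meant to be masked.

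7. **Which endpoint is affected.** The scale plainly serves the appearance endpoint in the End points list. No other photographic rating instrument is printed, so it might also serve primary measure (b). Against that, the design paragraph lists overall clinical appearance separately, among the other endpoints. The text does not decide the matter.

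**The case against.** The strongest reply is that the printed table may be only a layout for data capture. The headings reveal allocation only when a photograph is matched to a column, and a coded reading could come first. The working forms were to be electronic and piloted, attached forms are mentioned but not shown, and this is a summary document that asks for brief descriptions. This stands in part. A coded working form cannot be excluded, so a reader who infers that every rating in the trial was in fact unblinded goes further than the document allows. The conflict within the printed text remains, because nothing shown points to a coded version.

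A second reply is that blinding may be impossible anyway, since lasered skin can look different from control skin and a dressing may mark the graft. This also stands in part. How often laser effects would show is unclear: the CO2 laser risk table lists hypopigmentation as common, while the complications paragraph that follows calls pigment change uncommon. For the two lasered sites, however, the heading can disclose what the photograph does not.

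A third reply is that blinded might mean blinded only to whether a photograph is from before or after treatment. The protocol does not say so, and that would not mask the comparison between sites.

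A reader might also infer that a primary outcome is compromised. The document does not support that, because the link between this scale and primary measure (b) is left open. The lesion counts and the p53 histology do not use this form.

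**Conclusion.** Wrong as written. The form's title promises a blinded rater, and all three of its column headings disclose the allocation to anyone who completes it as printed. This contradicts the current text and is more than a detail left for a later document.

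The conclusion rests on two assumptions: that the rater completes the printed form directly, and that no coded working form exists outside the document. It covers at least the appearance endpoint and does not depend on the scale being a primary measure. The direction and size of any bias on the five-point score cannot be calculated from the protocol, so no numerical effect is claimed. The point deserves correction because the rating is subjective, the comparison in aim 2 is directly exposed and the remedy is cheap.

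**What to change.** - Head the rating columns Site A, Site B and Site C, with the order randomised separately for each subject.
- Give the rater photographs coded by site, without visit date and in random order.
- Have existing staff other than the rater hold the key and map scores to treatments after rating.
- State that only these masked photographic ratings will be reported as blinded, and that appearance scores given by the non-blinded investigator at visits will be reported separately as unblinded.
- If a coded working form already exists, one sentence describing it and who holds the key would be enough.

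The cost is a relabelled form, coded photo files and a key. No extra visits, photographs or evaluators are needed.

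The protocol should also state the limit of the remedy. Visible laser effects or a dressing over the graft may still reveal allocation, so coding mainly protects CO2 versus CO2 plus graft in photographs where the graft cannot be seen.
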